5.4.3. Management of Dose-Limiting Toxicities or Other Urgent Situations

In all cases, investigators may employ any measures or concomitant medications, after discussion with the medical monitor (whenever possible), necessary to optimally treat the subject.

5.4.4. Follow-Up of Dose-Limiting Toxicities

Any DLT should be followed until it resolves to baseline or appears to have stabilized for a minimum of 4 weeks (e.g., 28 days). During follow-up, subjects should be seen as often as medically indicated to assure safety.

5.4.5. Procedures for Cohort Review and Dose Escalation

Telephone conferences will be scheduled by the sponsor, or sponsor's delegate, with study investigators to review cohort-specific data and overall safety data, to agree on dose escalation, adjudicate individual high-grade AEs as potentially dose-limiting, and guide other major study decisions.

5.4.6. Criteria and Procedures for Dose Interruptions and Adjustments of Study Drug

Treatment with study drug may be delayed allowing for resolution of toxicity. Subjects may resume treatment if no medical condition or other circumstance exists that, in the opinion of the investigator, would make the subject unsuitable for further participation in the study. For toxicities that occur outside of the 28-day DLT period, the treating investigator should contact the medical monitor to discuss the case of any subject whose treatment has been delayed for more than 4 weeks (28 days).

Instructions for dose modifications and interruptions are outlined in [Table 4](#). Individual decisions regarding dose interruptions and reductions should be made using appropriate clinical judgment in consultation with the medical monitor, considering the relatedness of the AE to the study drug and the subject's underlying condition. Adverse events that have a clear alternative explanation or transient (≤ 72 hours) abnormal laboratory values without associated clinically significant signs or symptoms may be exempt from dose-reduction rules. Dose interruptions are permitted in the case of medical/surgical events or logistical reasons not related to study therapy (e.g., elective surgery, unrelated medical events, subject vacation, and/or holidays). Subjects should be placed back on study therapy within 4 weeks (28 days) of the scheduled interruption unless otherwise discussed with the medical monitor. The reason for interruption should be documented in the subject's study record.

Table 4: Rules for Interruption and Restarting of Study Drug

NCI CTCAE v5.0 Grade/Severity	Timing for Restarting Treatment	Dose Level for Restarting Treatment	Treatment Discontinuation
1-2 (mild-moderate)	Continue treatment at the discretion of the investigator.	N/A	N/A
3 (severe)	Toxicity resolves to Grade 0-1.	Reduce by 1 dose level. ^a	Toxicity does not resolve within 4 weeks (28 days) of last dose, except by approval of the medical monitor. OR Second occurrence of previously resolved Grade 3 AE.
4 (life-threatening)	Permanently discontinue.	N/A	Permanently discontinue.

Abbreviation: N/A = not applicable.

Note: Permanently discontinue for any severe or Grade 3 AE that recurs or any life-threatening event.

^aNo more than 2 dose reductions of study drug are permitted. Subjects should be permanently discontinued from study drug if they have AEs requiring more than 2 dose reductions of study drug.

5.4.7. Definition, Procedures, and Supportive Care Guidelines for Immune-Related Adverse Events

NC318 is an immune modulator, and although no significant toxicities were identified in preclinical models, it is possible that irAEs (both nonserious and serious) similar to those described with approved immunotherapies may occur. Adverse events of a potential immunologic etiology or irAEs may be defined as an AE consistent with an immune phenomenon associated with drug exposure *after all other etiologies have been eliminated*. Immune-related AEs may be expected based on the nature of NC318, its mechanism of action, and based on reported experience with other immunotherapies. Special attention should be paid to AEs that may be suggestive of potential irAEs. An irAE can occur shortly after the first dose or several months after the last dose of treatment. Suspected irAEs should be discussed with the medical monitor when possible. If there is any suspicion of potential cytokine-release syndrome (CRS), subjects should be treated per institutional policy.

Subjects should receive appropriate supportive care measures as deemed necessary by the treating investigator. Suggested supportive care measures for the management of drug-related AEs with potential immunologic etiology are outlined in [Table 5](#). Detailed supportive care guidelines for specific irAEs can be found in Brahmer et al. ([Brahmer 2018](#)). For each AE, attempts should be made to rule out other causes, including but not limited to metastatic disease or bacterial or viral infection, which might require specific supportive care.

Table 5: Supportive Care Guidelines for Subjects Exhibiting Immune-Related Adverse Events

NCI CTCAE v5.0 Grade/Severity	Supportive Care
Grade 1 (mild)	
Monitor symptoms and provide symptomatic treatment.
Grade 2 (moderate)	
Monitor symptoms and provide symptomatic treatment.Consider consultation with specialists as necessary.Consider systemic corticosteroids per institutional standard of care.
Grade 3 - 4 (severe–life-threatening)	
Monitor symptoms and provide symptomatic treatment.Consider consultation with specialists as necessary.Administer corticosteroids per institutional standard of care.More potent immunosuppressive therapies should be considered for events not responding to systemic steroids after discussing with the medical monitor.Study drug should be permanently discontinued for clinically significant or severe irAEs or for events where steroid course cannot be tapered below 7.5 mg/day prednisone or equivalent to manage symptoms.

Abbreviations: CTCAE = Common Terminology Criteria for Adverse Events; irAE = immune-related adverse event; NCI = National Cancer Institute.

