5.4.9. Criteria for Permanent Discontinuation of Study Drug

The occurrence of an unacceptable toxicity not caused by the underlying malignancy will be presumed to be related to study drug and will require that the study drug be permanently discontinued. Unacceptable toxicity is defined as follows:

- Grade 4 or a life-threatening AE
- \geq Grade 2 ocular irAE
- Occurrence of an AE that is related to treatment with the study drug that, in the judgment of the investigator or the sponsor's medical monitor, compromises the subject's ability to continue study-specific procedures, or is considered to not be in the subject's best interest.
- Persistent treatment related AE requiring a delay of study drug beyond 4 weeks (28 days)

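### Stopping and restart rules conflict for a first, resolved, non-ocular Grade 3 irAE, and for a treatment-related Grade 3 AE that delays dosing beyond 28 days

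*Combined protocol and SAP*

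**What the plan says.** Four places in the protocol bear on this.

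- **Section 5.4.6, Table 4**, titled as rules for interrupting and restarting study drug, is organised by CTCAE grade and applies to adverse events in general. Grade 3 carries the label severe. Restart is allowed when "Toxicity resolves to Grade 0-1", and the dose instruction is "Reduce by 1 dose level". Discontinuation follows if "Toxicity does not resolve within 4 weeks (28 days) of last dose, except by approval of the medical monitor", or on a second occurrence. The table note says: "Permanently discontinue for any severe or Grade 3 AE that recurs or any life-threatening event". The text above the table asks the investigator, for toxicities outside the DLT period, to "contact the medical monitor to discuss the case of any subject whose treatment has been delayed for more than 4 weeks (28 days".
- **Section 5.4.7, Table 5**, is introduced as "Suggested supportive care measures for the management of drug-related AEs with potential immunologic etiology". Its last row covers Grades 3 and 4 together, labelled severe to life-threatening, and states: "Study drug should be permanently discontinued for clinically significant or severe irAEs". The same sentence adds a second trigger: events whose steroid course cannot be tapered below 7.5 mg/day of prednisone or equivalent.
- **Section 5.4.9** defines unacceptable toxicity, for which permanent discontinuation is mandatory. The list includes Grade 4 or life-threatening events, ocular irAEs of Grade 2 or higher, related events that the investigator or medical monitor judges to rule out continuing, and "Persistent treatment related AE requiring a delay of study drug beyond 4 weeks (28 days".
- **Section 5.5.1** repeats that subjects with unacceptable toxicity must come off study drug. It gives no waiver for this, although it does give one for confirmed radiographic progression.

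**The concern.** A site following Table 4 and a site following Table 5 could treat the same Grade 3 irAE in opposite ways: one restarts at a lower dose, the other stops for good. A site following Table 4 could also keep a subject on study with the medical monitor's approval when Section 5.4.9 has already made stopping mandatory.

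This is first a safety matter. Sections 1.3.1 and 8.8 both name irAEs as the most likely class of toxicity. The Phase 2 regimen is also largely untested. Section 1.2.2 models exposure on 800 mg weekly as nearly ten times that on 400 mg every 2 weeks, and Section 1.3.3.1 reports only 4 subjects treated at 800 mg every 2 weeks.

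It is secondly a data matter. Safety and tolerability are the primary endpoint (Section 2.2.1). Inconsistent stopping would change how long subjects stay exposed, and so the adverse events they can go on to report, for reasons unrelated to the drug.

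**Working it through.** The plan gives no figure to reproduce here. The check sets the rules side by side, with a short calculation to align the two 28-day limits.

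**Part 1: Grade 3 irAE**

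1. Grade 4: Table 4, Table 5 and Section 5.4.9 all lead to a permanent stop. There is no conflict.
2. Ocular, Grade 2 or higher: Section 5.4.9 names it and makes the stop mandatory. There is no open question.
3. Non-ocular Grade 3, recurrent: Table 4 and its note require a permanent stop. There is no conflict.
4. Non-ocular Grade 3, first occurrence, resolved to Grade 0-1: Table 4 allows restart one level lower. Table 5, reading severe as both tables label it, says to stop permanently. Section 5.4.9 does not list this event and could reach it only through its judgment criterion. The conflict is here.
5. Table 5's own scope is uncertain. If severe means Grade 3, every event in the Grade 3-4 row already meets the first trigger and the steroid-taper trigger adds nothing. Either that clause is redundant, or severe means something narrower than Grade 3 and is not defined.

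**Part 2: delay beyond 28 days, treatment-related Grade 3 AE**

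Inputs: dosing interval of 7 days for Cycles 1-8 and 14 days from Cycle 9 (Section 6.2); Table 4 limit of 28 days from last dose; Section 5.4.9 limit of 28 days of delay. Assumption: delay is counted from the date the missed dose was due, which the protocol does not state.

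Days since last dose = dosing interval + delay.

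- Section 5.4.9 limit, weekly dosing: 7 + 28 = 35 days since last dose.
- Section 5.4.9 limit, two-weekly dosing: 14 + 28 = 42 days since last dose.
- Table 4 limit expressed as delay, weekly dosing: 28 - 7 = 21 days.
- Table 4 limit expressed as delay, two-weekly dosing: 28 - 14 = 14 days.

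Both 35 and 42 exceed 28. A treatment-related Grade 3 event that is still unresolved when it crosses the Section 5.4.9 limit has therefore already crossed the Table 4 limit. From then on Section 5.4.9 says stop, while Table 4 says stop unless the medical monitor approves otherwise. If delay is instead counted from the last dose, both limits fall at 28 days and the two outcomes still differ.

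**The case against.** The best defence on irAEs is that Table 4 is the default and the later sections give event-specific rules that override it. Table 6 follows that pattern: a Grade 3 infusion reaction is a permanent stop there, although Table 4 would allow a restart and makes no exception for infusion reactions. On this reading only a cross-reference is missing. The reading is reasonable, but the protocol does not state it. Table 5 is introduced as suggested care and uses should, whereas Table 4 is titled as rules. Section 5.4.9, the natural place for an override, omits non-ocular Grade 3 irAEs.

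On the delay, the Table 4 waiver can be given a role of its own: between its limit and that of Section 5.4.9 (delays of 21 to 28 days on weekly dosing, 14 to 28 on two-weekly), with Section 5.4.9 as the outer bound. It also covers unrelated events, which the Section 5.4.9 delay criterion does not. That stands as a possible intent, but Table 4 puts no end date on the waiver. The Section 5.4.6 request to discuss long delays is not itself a waiver, but it does not tell the investigator that stopping is mandatory either.

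Medical monitor involvement in dose decisions and suspected irAEs should reduce variation between sites. It does not settle which text the monitor should apply.

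A reader might infer that every Grade 3 irAE and every delay over 28 days is governed by contradictory rules. The documents do not support that. Ocular and recurrent Grade 3 irAEs are settled, Table 5's reach over Grade 3 is itself unclear, and the Table 4 waiver appears only in the Grade 3 row.

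**Conclusion.** Two conflicts stand in the current text, each narrow. The first concerns a first, resolved, non-ocular Grade 3 irAE: Table 5 against Table 4, with no stated precedence and with Table 5's own scope unclear. The second concerns a persistent treatment-related Grade 3 AE with a delay beyond 28 days: Sections 5.4.9 and 5.5.1 against the Table 4 waiver, with limits that may lie 7 or 14 days apart depending on the dosing schedule and on how delay is counted.

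The effect on trial results cannot be sized, because the available text gives no count of Grade 3 irAEs or of long delays. It may be tempting to express one event as a percentage of a 17-subject subgroup, but that would measure only the weight of one subject. Seventeen is also the evaluable maximum if Stage 2 opens, whereas safety is summarised on the safety analysis set. The link to the primary endpoint is indirect, since that endpoint counts adverse events and not discontinuations.

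The sample size and the Simon rules are not affected. The point should be corrected because these are operative safety instructions. The first conflict rests on reading severe as Grade 3, as both tables and Appendix 2 label it. The second does not depend on how delay is counted.

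**What to change.** Reconcile Table 4 and the text of Section 5.4.6, Table 5 in Section 5.4.7, Section 5.4.9 and Section 5.5.1. The amendment should state:

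1. which provision governs a non-ocular Grade 3 irAE, and what severe and the steroid-taper clause mean within the Grade 3-4 row of Table 5;
2. whether the 4-week limit can be waived for a treatment-related event and, if so, by whom, with the same answer in all the places listed above;
3. the date from which the 28 days run.

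Add cross-references so that a site reading any one provision is led to the others. The content of the rules is a clinical decision for the sponsor and investigators, and this review takes no position on it. The cost is amendment wording, with no change to sample size or analysis.

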5.4.8. Management of Infusion Reactions

Table 6 shows treatment guidelines for subjects who experience an infusion reaction associated with administration of study drug. Signs and symptoms usually develop during or shortly after drug infusion and generally resolve completely within 24 hours of completion of infusion. As of 29-SEP-2021 data cutoff, there were 4 with infusion reactions (two grade 1 [n=2] and two grade 2 [n=2]) amongst subjects from Phase 1 study (n=49) and 7 had infusion reactions (Grade 1 [n= 1], Grade 2 [n=5], and Grade 3 [n=1]) amongst subjects from Phase 2 study (n=43).

Table 6: Infusion Reaction Treatment Guidelines

NCI CTCAE v5.0 Grade/Severity	Treatment	Premedication at Subsequent Dose Administration
Grade 1: Mild reaction; infusion interruption not indicated; intervention not indicated.	Increase monitoring of vital signs as medically indicated until the subject is deemed medically stable in the opinion of the investigator.	None.
Grade 2: Requires therapy or infusion interruption but responds promptly to symptomatic treatment (e.g., antihistamines, NSAIDs, narcotics, IV fluids); prophylactic medications indicated for \leq 24 hours.	
Stop infusion and monitor symptoms. Additional appropriate medical therapy may include but is not limited to the following:
 
• IV fluids• Antihistamines• NSAIDs• Acetaminophen• Narcotics 
Increase monitoring of vital signs as medically indicated until the subject is deemed medically stable in the opinion of the investigator. If symptoms resolve within 1 hour of stopping drug infusion, the infusion may be restarted at 50% of the original infusion rate. Otherwise, dose administration will be interrupted until symptoms resolve, and the subject should be premedicated for the next scheduled dose. Subjects who develop Grade 2 toxicity despite adequate premedication should be permanently discontinued from further study drug administration.
	
Subject may be premedicated 1.5 h (\pm 30 min) prior to infusion with the following:
 
• Diphenhydramine 50 mg orally (or equivalent dose of antihistamine).• Acetaminophen 500-1000 mg orally (or equivalent dose of antipyretic).

NCI CTCAE v5.0 Grade/Severity	Treatment	Premedication at Subsequent Dose Administration

Grade 3: Prolonged (i.e., not rapidly responsive to symptomatic medication and/or brief interruption of infusion); recurrence of symptoms following initial improvement; hospitalization indicated for other clinical sequelae (e.g., renal impairment, pulmonary infiltrates). OR Grade 4: Life-threatening; pressor or ventilatory support indicated.
	
Stop infusion. Additional appropriate medical therapy may include but is not limited to:
 
• IV fluids• Antihistamines• NSAIDs• Acetaminophen• Narcotics• Oxygen• Pressors• Corticosteroids• Epinephrine 
Increase monitoring of vital signs as medically indicated until the subject is deemed medically stable in the opinion of the investigator. Hospitalization may be indicated. Subject is permanently discontinued from further study drug administration.
	No subsequent dose.

Abbreviations: CTCAE = Common Terminology Criteria for Adverse Events; NCI = National Cancer Institute.

5.4.9. Criteria for Permanent Discontinuation of Study Drug

The occurrence of an unacceptable toxicity not caused by the underlying malignancy will be presumed to be related to study drug and will require that the study drug be permanently discontinued. Unacceptable toxicity is defined as follows:

- Grade 4 or a life-threatening AE
- \geq Grade 2 ocular irAE
- Occurrence of an AE that is related to treatment with the study drug that, in the judgment of the investigator or the sponsor's medical monitor, compromises the subject's ability to continue study-specific procedures, or is considered to not be in the subject's best interest.
- Persistent treatment related AE requiring a delay of study drug beyond 4 weeks (28 days)

5.4.10. Treatment After Initial Evidence of Radiologic Disease Progression

Immunotherapeutic agents may produce antitumor effects by potentiating endogenous cancer-specific immune responses. The response patterns seen with such an approach may extend beyond the typical time course of responses seen with cytotoxic agents and may manifest as a clinical response after an initial increase in tumor burden or even the appearance of new lesions. As a result, scans showing progressive disease should be repeated within 4-6 weeks to rule out pseudoprogression at the discretion of the PI.

If radiologic imaging shows disease progression, then subjects have the option to continue treatment while awaiting radiographic confirmation of progression as outlined in [Section 7.6.1](#).

5.5. Withdrawal of Subjects from Study Drug

5.5.1. Withdrawal Criteria

A subject may withdraw consent at any time for any reason or be removed from the trial at the discretion of the investigator should any untoward effect occur. In addition, a subject may be withdrawn by the investigator or the Sponsor if enrollment into the trial is inappropriate, the trial If a subject is withdrawn, then every reasonable effort should be made to determine the reason for withdrawal, and this information should be recorded in the eCRF.

Discontinuation of study treatment does not represent withdrawal from the study. A subject may discontinue from treatment but agree to remain on-study, as long as the subject does not withdraw consent.

Subjects must be withdrawn from the trial for any of the following reasons:

- The subject is lost to follow-up
- Consent is withdrawn for study (does not agree to follow-up); no additional data collection should occur

Subjects must discontinue from the study treatment but can continue to be monitored for any of the following reasons:

- The subject becomes pregnant
- Consent is withdrawn for further treatment (agrees to follow-up)
- Further participation would be injurious to the subject's health or well being
- Unacceptable toxicity ([Section 5.4.9](#)). Subjects with unacceptable toxicities must be withdrawn from study drug but will continue to be followed during the safety follow-up visits as specified in [Section 6.4](#)
- The study is terminated by the local IRB or regulatory authority
- The study is terminated by the sponsor
- Confirmed radiographic progression of disease per RECIST v1.1. (except if Sponsor approves treatment continuation)
- Investigator decision to withdraw subject
- If, during the course of the study, a subject is found not to have met eligibility criteria, then the medical monitor in collaboration with the investigator, will determine whether the subject should be withdrawn from the study
- If the subject is noncompliant with study procedure or study drug administration in the investigators opinion then the Sponsor should be consulted for instruction on handling the subject.

Subjects who discontinue study treatment but agree to remain on-study should continue to be followed according to the applicable Post-Treatment Follow-up schedule.

5.5.2. Withdrawal Procedures

If the decision is made to permanently discontinue the study drug, the subject will be withdrawn from the study, and the end-of-treatment (EOT) visit should be conducted. Reasonable efforts should be made to have the subject participate in the follow-up period. The date on which the decision was made to discontinue study treatment and the reason for treatment discontinuation will be recorded in the eCRF.

If a subject discontinues study treatment, the site monitor and Sponsor must be notified.

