- COVID-19 vaccine within 14 days prior to receiving the first dose of the study drug *and* during the 28-day DLT period. Note: For 2-dose COVID-19 vaccines, subjects must wait at least 14-days after 2nd vaccine dose administration.

Subjects who, in the assessment by the investigator, require the use of any of the aforementioned treatments for clinical management should be removed from the study. Subjects may receive other medications that the investigator deems to be medically necessary. The exclusion criteria describe other medications that are prohibited in this study.

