9.5.4. Efficacy Analyses

The response will be assessed by CT/MRI image during screening and every 8 weeks (\pm 7 days) post-dosing for 6 months and then every 12 weeks (\pm 7 days) thereafter (or per standard of care). The efficacy study endpoints include ORR, DCR, DoR, PFS, and OS. Tumor response will be determined according to RECIST v1.1. Time-to-event data (DoR, PFS, and OS) will be analyzed using the Kaplan-Meier method. All the efficacy data will be summarized by phase, dose group, and cohort.

- ORR includes RECIST v1.1 complete and partial response (CR or PR). ORR with 95% exact CI will be summarized by phase, dose group, and cohort.
- DCR includes RECIST v1.1 complete, partial response, and stable disease (CR, PR or stable disease). DCR with 95% exact CI will be summarized by phase, dose group, and cohort.
- DoR is defined as the duration from the first documented ORR to the first documented progressive disease or death due to any cause, whichever occurs first. For subjects who are alive and progression-free at the time of discontinuation from study, data cutoff for analysis, or use of other anti-cancer drug, DoR will be censored at the last tumor assessment date.

The DoR will only be analyzed for the subgroup of subjects with an objective response.

DoR = (progressive disease, death, or censored date) – (date of first response + 1)

- PFS is defined as from starting study treatment to the first documented progressive disease or death due to any cause, whichever occurs first. For subjects who are alive and progression-free at the time of discontinuation from study, data cutoff for analysis, or use of other anti-cancer drug, DOR will be censored at the last tumor assessment date.

PFS = (progressive disease, death, or censored date) – (date of first dose of study drug + 1)

- OS is defined as from starting study treatment to death due to any cause. For subjects who are alive at the time of discontinuation from study or data cutoff for analysis, OS will be censored at the date of last known alive (LKA).

OS = (Death or LKA date) – (date of first dose of study drug + 1)

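### Section 5.5.2 withdraws a subject from the study when study drug is permanently stopped, against 5.5.1, and Section 9.5.4 uses an undefined study discontinuation to trigger censoring of DoR, PFS and OS

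*Combined protocol and SAP*

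**What the plan says.** Section 5.5.1 separates stopping treatment from leaving the study: "Discontinuation of study treatment does not represent withdrawal from the study". It gives two reasons for mandatory withdrawal from the trial, namely loss to follow-up and withdrawal of consent that includes follow-up. For everyone else it says: "Subjects who discontinue study treatment but agree to remain on-study should continue to be followed according to the applicable Post-Treatment Follow-up schedule".

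Section 5.5.2 then says: "If the decision is made to permanently discontinue the study drug, the subject will be withdrawn from the study". The same sentence calls for the end-of-treatment visit, and the next one reads: "Reasonable efforts should be made to have the subject participate in the follow-up period".

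Section 5.6.3 says that subjects who need one of the listed prohibited therapies "should be removed from the study". Earlier in the same section, stopping study drug is only a possible consequence of such a need.

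Section 9.5.4 sets the censoring rules. For both DoR and PFS the trigger is: "For subjects who are alive and progression-free at the time of discontinuation from study, data cutoff for analysis, or use of other anti-cancer drug". In the DoR bullet the rule ends: "DoR will be censored at the last tumor assessment date". The PFS bullet repeats this and also names DoR, an apparent slip for PFS. For OS the rule is: "For subjects who are alive at the time of discontinuation from study or data cutoff for analysis, OS will be censored", with the date last known alive as the censoring date. Section 9.5.4 does not say what counts as discontinuing the study.

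**The concern.** Two sections give opposite answers to one question: is a subject who has permanently stopped drug still on study? Normally that is an editorial matter. Here the answer feeds a censoring rule, so the same patients can yield different PFS, DoR and OS estimates depending on which section the site or the programmer follows. Section 5.5.2 carries the title on withdrawal procedures, so it is the one a site is likely to consult when a subject stops drug.

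Subjects who stop for toxicity or clinical decline may have a different prognosis from those who continue. If their prognosis is worse, censoring them around drug stop would make the Kaplan-Meier curves too favorable.

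**Working it through.** No arithmetic in the plan applies: it states no event count, power or sample size for PFS, DoR or OS. The check is to compare the sections and then trace the censoring rules.

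**Is the subject on study after drug stop?**

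| Section | Position |
|---|---|
| 5.5.1 | Yes, unless lost to follow-up or consent is withdrawn for follow-up |
| 5.5.2 | No, though follow-up is still to be sought |
| 6.4.1 and Table 7 footnote b | Yes: imaging continues if drug stopped for a reason other than progression |
| 6.4.2 and Table 7 footnote c | Yes: survival contact about every 3 months after progression or new anticancer therapy |
| 7.6.1.4 | Yes: imaging continues at the protocol interval |
| 10.3 | Non-completion means consent withdrawn or lost to follow-up; drug stop is not listed |

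Section 5.5.2 stands alone, and its own follow-up sentence sits awkwardly with its first clause.

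**What 9.5.4 does if 5.5.2 is taken literally.** Drug stop then counts as discontinuing the study.

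- *PFS, and DoR for responders.* A subject alive and progression-free at drug stop meets the trigger and is censored at the last tumor assessment. Subjects who stop because of documented progression already have their event and are unaffected.
- *OS.* Any subject alive at drug stop meets the trigger, including one who stopped for progression, and is censored at the date last known alive.

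**Hypothetical subject, for illustration only.** Drug is stopped for toxicity at month 2, progression follows at month 5 and death at month 10.

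- Under 5.5.1: PFS event at month 5, OS event at month 10.
- Under 5.5.2 read literally: no PFS event. Table 7 footnote p places the discontinuation scan within 4 weeks either side of drug stop, so the PFS censoring date could fall near month 2, before or after it. If imaging continues, the date could be later, because 9.5.4 does not say whether the last assessment must precede study discontinuation.
- Under 5.5.2 read literally: no OS event. If all contact ceased, the date last known alive would be about month 2. If 3-monthly contacts continued, it would move to month 2 + 3 + 3 = 8. Either way the death at month 10 would not count.

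**Section 5.6.3.** For PFS and DoR it adds little: other anticancer drugs already trigger censoring under 9.5.4, and palliative radiation already counts as progression for PFS under 5.6.3. What remains is OS, where removal from the study conflicts with the survival follow-up that 6.4.2 gives to subjects who start new anticancer therapy.

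**The case against.** The best case for the plan is that 5.5.2 contains a slip of wording. Its parent heading concerns withdrawal from study drug. The date it sends to the eCRF is that of the decision to stop treatment, not a study-discontinuation date, and it asks for follow-up in the next sentence. Several other sections order imaging or survival contact after drug stop, and 6.4.2.1 lets the sponsor request survival status for subjects without scheduled contact. Section 10.3 comes close to the definition that 9.5.4 lacks, and the introduction to Section 9 leaves further detail to a SAP.

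Most of this stands as evidence of intent. It does not remove the contradiction from the current text, and it does not supply the missing definition. Continued follow-up alone is no cure, because a death found in follow-up would still come after study discontinuation on the literal reading.

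A reader might go further and infer that every subject who stops drug will be censored at the stop date for all three endpoints. The documents do not support that. Study discontinuation is the trigger, while the censoring date is the last tumor assessment or the date last known alive. Subjects who stop for progression already have their PFS or DoR event, and DoR concerns responders only. A reader might also infer that PFS, DoR and OS will be overstated. That would need discontinuation rates, reasons for stopping and the prognosis of those subjects, none of which is given.

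**Conclusion.** The contradiction is real and lies in the operative text. Together with the undefined trigger in 9.5.4, it permits an analysis in which progressions and deaths after drug stop are not counted. Whether that happens depends on which section is followed and on how study discontinuation is recorded and programmed.

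The size cannot be stated. The group exposed is, for OS, subjects alive at drug stop; for PFS, those who stop alive and progression-free; for DoR, the responders among the latter. An upward bias rests on the assumption that subjects who stop for toxicity or decline do worse than those who remain.

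The consequence is limited. PFS, DoR and OS are secondary and descriptive, and Section 9.3 plans no formal test. The Simon stage decisions in 9.2.2 rest on responses, so no error rate, sample size or stage decision changes. The point should be corrected because Kaplan-Meier estimates of these endpoints will be reported and the correction is simple.

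**What to change.** 1. Reconcile 5.5.2 with 5.5.1 and 6.4, so that permanently stopping study drug ends treatment only and the subject stays on study for post-treatment follow-up.
2. In 9.5.4, define study discontinuation, for censoring purposes, as withdrawal of consent for follow-up or loss to follow-up. This agrees with 5.5.1 and 10.3.
3. In the PFS bullet of 9.5.4, change the quantity censored from DOR to PFS.
4. Reconcile 5.6.3 with itself and with 6.4.2. One part of 5.6.3 removes subjects from the study and another treats stopping study drug as a possibility only, while 6.4.2 keeps subjects who start new anticancer therapy under survival follow-up. What happens to treatment in these cases is for the sponsor and investigators to settle; the request here is only that the passages agree.

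The cost is wording. Sample size, visits and data collection do not change, because the follow-up is already specified in 6.4 and 7.6.1.4.
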